3.1 Primary objectives and endpoints

Primary objective 1:

To evaluate the safety and tolerability of BG505 MD39.3 trimer mRNA vaccines in healthy, HIV-uninfected adults

Primary endpoint 1:

Local and systemic reactogenicity signs and symptoms for a minimum of seven days following receipt of any study product. Laboratory measures of safety. All adverse events (AEs) for thirty days after receipt of study vaccination

All serious adverse events (SAEs), medically attended adverse events (MAAEs), adverse events of special interest (AESIs), and AEs leading to early participant withdrawal or permanent discontinuation will be collected throughout the study

Primary objective 2:

To evaluate the ability of BG505 MD39.3 trimer mRNA vaccines to elicit autologous neutralizing antibodies and to compare responses between the membrane-bound vaccine regimen (BG505 MD39.3 gp151 mRNA) and the membrane-bound knockout (BG505 MD39.3 gp151 CD4KO mRNA) and between the membrane-bound vaccine regimen (BG505 MD39.3 gp151 mRNA) and the soluble trimer (BG505 MD39.3 mRNA) vaccine arms, within each dose level

Primary endpoint 2:

Occurrence, magnitude, and response rate of serum antibody neutralization of a vaccine-matched tier 2 HIV-1 strain as measured by the TZM-bl assay two weeks after the third vaccination

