3.2 Secondary objectives and endpoints

Secondary objective 1:

To evaluate the ability of BG505 MD39.3 trimer mRNA vaccines to elicit humoral and cellular immune responses and to compare responses between the membrane-bound vaccine regimen (BG505 MD39.3 gp151 mRNA) and the membrane-bound knockout (BG505 MD39.3 gp151 CD4KO mRNA) and between the membrane-bound vaccine regimen (BG505 MD39.3 gp151 mRNA) and the soluble trimer (BG505 MD39.3 mRNA) vaccine arms, within each dose level and to compare responses between dose levels for each vaccine regimen

Secondary endpoints 1:

- Occurrence, magnitude, and response rate of serum antibody neutralization of a vaccine-matched tier 2 HIV-1 strain as measured by the TZM-bl assay two weeks after the second vaccination
- Occurrence, magnitude, and response rate of serum IgG binding antibodies to the BG505 trimer, and specific epitopes (base of trimer, V3, internal epitope) as measured by binding antibody multiplex assay (BAMA) two weeks after the second and third vaccination
- Occurrence, magnitude, and response rate of CD4+ T-cell responses as assessed by intracellular cytokine staining assays (ICS) two weeks after the third vaccination

Secondary objective 2:

To evaluate the durability of humoral immune responses to BG505 MD39.3 trimer mRNA vaccines and to compare durability between arms

Secondary endpoints 2:

- Occurrence, magnitude, and response rate of serum antibody neutralization of a vaccine-matched tier 2 HIV-1 strain, as measured by the TZM-bl assay six months after the third vaccination
- Occurrence, magnitude, and response rate of serum IgG binding antibodies to the BG505 trimer, and specific epitopes (base of trimer, V3, internal epitope), as measured by BAMA six months after the third vaccination

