As shown in [Table 6-2](#), there is limited power for a formal comparison of immunogenicity response rates between vaccine arms of size n = 15. For either 80% or 90% power, the sizes of differences that the trial is powered to detect are large. These calculations use a Fisher's exact 2-sided test with a Type I error rate of 0.05. The trial is, however, adequately powered to detect group differences based on data from a study in rabbits led by [name]. There is 90% power to detect an 11-fold difference in ID50 pseudovirus neutralization and a 1.9-fold difference in serum binding responses between two dose groups or between two dose levels of n=15 evaluable samples each. For the comparisons of BG505 MD39.2 gp151 mRNA vs. BG505 MD39.3 mRNA (or vs. BG505 MD39.3 gp151 CD4KO mRNA) that aggregate arms over the low and high dose levels, the trial has 90% power to detect a 5.2-fold difference in ID50 pseudovirus neutralization and a 1.6-fold difference in serum binding responses between two groups, aggregated over dose level (n=30 evaluable samples in each of the aggregated groups). These calculations use a two-sided t-test with a Type I error rate of 0.05 and estimated standard deviation of 0.85 for log10 ID50 values and of 0.23 for ELISA AUC MD39 at day 182 (shown in [Figure 6-2](#)). The standard deviation estimates were based on the mean standard deviation across four groups of rabbits, with n=6 per group, given either soluble or membrane-bound MD39.3 or MD39.2 vaccine at 2 weeks after 3rd vaccination.

Table 6-2 Power for comparison of response rates between 2 arms (n1 = n2 = 15)

True response rate Arm 1 (%)	Minimum true response rate in Arm 2 in order to detect a difference	
	80% power	90% power
10	64	71
20	76	82
30	85	90
40	92	95
50	97	99

[figure not shown]

Figure 6-2 Effect size necessary to detect a difference between groups for n=3 to 20 per group.
Estimated standard deviation of \log_{10} ID50 values from day 182 is 0.85 (left). Estimated standard deviation of ELISA AUC MD39 is 0.23 (right). The two figures are identical except for the y-axis scale which depends on the outcome-specific estimated standard deviation

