6.3.4 Immunogenicity analyses

6.3.4.1 General approach

For the statistical analysis of immunogenicity endpoints, data from enrolled participants will be used according to the initial randomization assignment regardless of how many injections they received. Additional analyses may be performed, limited to participants who received all scheduled injections per protocol. Assay results that are unreliable are excluded; results from specimens collected outside of the visit window, or from HIV-infected participants post-infection, may be excluded. Since the exact date of HIV infection is unknown, any assay data from blood draws 4 weeks prior to an infected participant's last seronegative sample and thereafter may be excluded. If an HIV-infected participant does not have a seronegative sample postenrollment, then all data from that participant may be excluded from the analysis.

Discrete categorical assay endpoints (eg, response rates) will be analyzed by tabulating the frequency of positive response for each assay by antigen and treatment arm at each timepoint for which an assessment is performed. Crude response rates will be presented with their corresponding 95% confidence interval estimates calculated using the score test method (40). Barnard or Fisher's exact tests, as specified in the SAP, will be used to compare the response rates of any 2 vaccine arms, with a significant difference declared if the 2-sided p-value is ≤ 0.05 . In general Barnard's is preferred since under most circumstances it is more powerful than Fisher's exact test (41).

For quantitative assay data (eg, percentage of positive cells from ICS assay), graphical and tabular summaries of the distributions by antigen, treatment arm, and timepoint will be made. For all primary and secondary immunogenicity endpoints, box plots and plots of estimated reverse cumulative distribution curves will be used for graphical display of all of the study arms. Typically, the results will be shown for each vaccine arm.

The difference between arms at a specific timepoint will be tested with a nonparametric Wilcoxon rank sum test if the data are not normally distributed and with a 2-sample t-test if the data appear to be normally distributed. The primary

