If a substantial amount of immunogenicity data are missing for an endpoint (at least 1 value missing from more than 20% of participants), then using the methods that require the MCAR assumption may give misleading results. In this situation, analyses of the immunogenicity endpoints at a specific timepoint will be performed with methods such as targeted minimum loss-based estimation (TMLE), parametric generalized linear models fit by maximum likelihood, augmented inverse probability weighting (AIPW) methods or multiple imputation methods. TMLE and AIPW are typically preferred because they are doubly robust, providing consistent estimation and appropriate inferences if either the outcome regression or the probability of observing the response value are modeled correctly, under the assumption that the missing data are missing at random (MAR). MAR assumes that the probability of an observation being missing only depends upon the observed responses and upon observed covariates, but not upon any unobserved data. TMLE methods will typically be implemented with the drtmle R package (46) available at CRAN, and will entail specification of a library of learners for the outcome regression and for the probability of observing the response value. When data are not missing at random, sensitivity analyses may be performed as an exploratory analysis. For assessing repeated immunogenicity measurement, linear mixed effects models will be used. If the immunological outcomes are left- and/or right- censored, then the linear mixed effects models of Hughes (47) will be used, because they accommodate the censoring. In addition, secondary analyses of repeated immunogenicity measurements may be done using weighted GEE (48) methods, which are valid under MAR. All of the models described above in this paragraph will include as covariates all available baseline predictors of the missing outcomes.

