
The occurrence and magnitude of serum antibody neutralization of pseudoviruses (BG505 MD39.3, BG505 MD39.3 gp151, and BG505 MD39.3 gp151 CD4KO) measured by the TZM-bl assay, the occurrence and magnitude of serum IgG binding antibodies to BG505 trimer, and specific epitopes (base of trimer, V3, internal epitope) measured by ELISA and/or BAMA, and the response rate and magnitude of CD4+ T-cell responses measured by intracellular cytokine staining assays (ICS) will be summarized using descriptive statistics. Data will be tabulated and graphically displayed by visit number and by number of doses received.

Discrete categorical assay endpoints (eg, response rates) will be analyzed by tabulating the frequency of positive response. Crude response rates will be presented with their corresponding 95% confidence interval estimated based on the score test method (40). Barnard’s exact tests may be employed to compare the response rates of immune responses between groups.

Quantitative assay endpoints will be summarized by time point. Nonparametric paired comparisons will be performed using Wilcoxon signed-rank tests, and the Wilcoxon rank sum test will be used to compare independent samples. More details of the analyses of each assay will be provided in the statistical analyses plan (SAP).

6.3.4.3 Analysis of CD4+ and CD8+ T-cell responses as measured by the ICS assay

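### Secondary objective 2 compares durability between arms, but its only endpoints are Month 12 levels and response rates, so a between-arm difference mixes the peak with the decline

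*Protocol*

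**What the plan says.** Protocol 3.2 states the second secondary objective as "To evaluate the durability of humoral immune responses to BG505 MD39.3 trimer mRNA vaccines and to compare durability between arms". Two endpoints serve it. One is neutralization of a vaccine-matched tier 2 strain "as measured by the TZM-bl assay six months after the third vaccination". The other is binding IgG "as measured by BAMA six months after the third vaccination". Each is defined as occurrence, magnitude and response rate at that visit. No change from peak, slope, half-life or persistence among peak responders is named.

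Peak measurements by the same assays exist. Primary endpoint 2 is neutralization "as measured by the TZM-bl assay two weeks after the third vaccination", and secondary endpoints 1 include BAMA binding at the same visit. Neither is linked to secondary objective 2.

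On analysis, Protocol 6.3.4.1 says "The difference between arms at a specific timepoint will be tested with a nonparametric Wilcoxon rank sum test" (or a t-test if the data look normal). Later in that section, in the paragraph on missing data, it says "For assessing repeated immunogenicity measurement, linear mixed effects models will be used", with a censored version when outcomes are censored. Protocol 6.3.4.2 adds "Nonparametric paired comparisons will be performed using Wilcoxon signed-rank tests". The SAP supplied covers safety only (SAP section 2) and defines no durability analysis.

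**The concern.** The objective has two parts: to evaluate durability, and to compare it between arms. The endpoints serve the first part. For the second they give only a level at one late visit, which depends on how high the response rose as well as on how fast it fell.

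If two arms decline at the same rate, the expected ratio between them at Month 12 equals their ratio at the peak. The Month 12 test then largely repeats the Month 6.5 comparison. In the other direction, an arm with a higher peak and a steeper fall can show no difference at Month 12. A reader of the final report could not tell a peak effect from a persistence effect, although both visits are sampled and assayed.

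Peak differences are what the trial looks for. Protocol 6.1.1 is powered for an 11-fold difference in ID50.

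**Working it through.** **Inputs (Protocol 6.1.1).** SD 0.85 for log10 ID50, from four groups of six rabbits two weeks after dose 3; 15 evaluable of 18 per arm; "These calculations use a two-sided t-test with a Type I error rate of 0.05". The documents give no within-person correlation between visits, so 0.5, 0.7 and 0.9 are assumed.

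**1. The plan's own figure.** The standard error of a difference in means is 0.85 × √(2/15) = 0.310. For an 11-fold ratio, log10(11) = 1.041, so the noncentrality is 1.041/0.310 = 3.36. With 28 degrees of freedom and critical value 2.048, power is 89.9%. The stated 90% reproduces.

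**2. Month 12 level test when the decline is identical.** Level at Month 12 = peak − decline. With equal declines, the expected log10 difference at Month 12 is log10(peak ratio), and step 1 applies unchanged, assuming the SD of 0.85 also holds at Month 12:

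| Peak ratio | log10 ratio | Noncentrality | Significant |
|---|---|---|---|
| 2 | 0.301 | 0.97 | 16% |
| 3 | 0.477 | 1.54 | 32% |
| 4 | 0.602 | 1.94 | 47% |
| 11 | 1.041 | 3.36 | 90% |

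Simulation agrees at the ratios run (2-, 3- and 11-fold). The Wilcoxon test gives about 87–88% at 11-fold. A t-test on each participant's change stays at about 5% for every peak ratio and correlation tried, as long as no value is censored.

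**3. The opposite case.** If one arm has a 5-fold higher peak and a 5-fold steeper decline, the Month 12 levels are equal and the level test rejects at 5%. The SD of the change is 0.85 × √(2(1 − ρ)) = 0.850, 0.658 or 0.380 for ρ = 0.5, 0.7 or 0.9. A test of the change then has 58%, 80% or over 99% power. The example is built to cancel exactly and is illustrative only.

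**4. Assay floor.** Protocol 2.2.2.2 treats ID50 above 10 as detectable in macaques and reports 0 of 6 and 2 of 6 neutralizers at week 26 in two of the mRNA groups, so many values may sit at the floor. A participant below it at both visits has a recorded change of zero. Simulations assume a floor of 10, ρ = 0.7 and an identical true decline of 0.7 log10:

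- 11-fold peak ratio, lower arm's mean peak about 32 or 100: a raw change test rejects in 21% or 10% of trials. The level test rejects in 84% or 88%.
- Peak response rates of 33% versus 67%, or 10% versus 50%: the raw change test rejects in 28% or 43%, in favour of the weaker arm.

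In further runs with the same floor and correlation, the raw change test rejected in about 31–34%, and the arm-by-visit test from a censored model in about 6–8%. There were only 120 runs per scenario, so the Monte Carlo error at 5% is √(0.05 × 0.95/120) ≈ 2 percentage points, and normality held by construction.

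**5. Precision of the change contrast.** Uncensored, with 15 per arm, the 90%-detectable difference in fold-decline is 11-fold, 6.4-fold or 2.9-fold at ρ = 0.5, 0.7 or 0.9.

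**6. Timing.** In Appendix D, dose 3 is targeted at Day 169 and Visit 15 at Day 365, a gap of 196 days. Both windows run from Day 1, ±21 and ±28 days at their allowable limits, so the gap can range from 196 − 49 = 147 to 196 + 49 = 245 days.

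**The case against.** The strongest reply is that the level retained at a late visit is a fair meaning of durability, and one the protocol itself uses. Its introduction aims at antibody levels that are sustained and protective, and section 2.4 cites titres held for a year with another mRNA vaccine. On that meaning, two arms with equal Month 12 levels are correctly called equal. This stands, and it is why the Month 12 endpoints should remain.

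Second, 6.3.4.1 already commits to mixed models for repeated measurements, and these assays are repeated. That supplies a model class but names no durability contrast and no arm-by-time term. The signed-rank tests in 6.3.4.2 are paired, and so do not compare decline between arms. An immunogenicity SAP may say more. The one supplied does not cover immunogenicity, so the gap is shown for the protocol only.

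Third, a change analysis has low precision at 15 per arm and is awkward when many titres are undetectable. Both points are right. They rule out a raw change score and limit what the added contrast can show.

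A reader might infer that the plan will report the higher-peak arm as more durable. The documents do not say so: both endpoints are openly labelled as six-month values, and significance is far from certain at modest peak ratios. A reader might also infer that the Month 12 level is the wrong endpoint and should be replaced. That does not follow either.

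**Conclusion.** The gap is real and bounded. Protocol 3.2 sets out to compare durability between arms with endpoints that do not separate peak from decline, and no other section supplied closes it. Under identical decline, the chance of a significant Month 12 difference runs from 16% at a 2-fold peak ratio to 90% at 11-fold. Those figures assume uncensored, roughly normal log10 titres and a rabbit SD carried over to human Month 12 data; with the assumed floor, the 11-fold figure was 84–88%. The within-person correlation is assumed throughout. Confidence is high on the mismatch between objective and endpoint and lower on its size in human data.

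**What to change.** Keep the Month 12 level and response rate in 3.2 as persistence endpoints. Add a between-arm comparison of the change in log10 ID50 and in BAMA magnitude from Visit 12 (Month 6.5) to Visit 15 (Month 12). Estimate it by the arm-by-visit term of the censored linear mixed model already cited in 6.3.4.1, with actual time since dose 3 in the model. State that a raw change score will not be used, that a difference in decline will be concluded only from this contrast, and that the number undetectable at both visits will be reported by arm.

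The cost is wording in the protocol and the immunogenicity analysis plan, and one model per assay; there are no new visits, samples or assays. The downsides are the low precision shown above and, when many values are censored, an estimate that leans on distributional assumptions. Both should be stated beside the result.

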3.3 Exploratory objectives

Exploratory objective 1

To determine whether higher doses of BG505 MD39.3 trimer mRNA vaccines induce stronger and/or more consistent humoral and/or cellular immune responses

Exploratory objective 2

To evaluate the epitope specificity of autologous (BG505/T332N) neutralization

Exploratory objective 3

To evaluate serum antibody specificities and elicitation of trimer degrading antibodies by electron microscopy-based polyclonal epitope mapping (EMPEM)

Exploratory objective 4

To evaluate the magnitude and kinetics of BG505-specific GC B and T-cell responses

Exploratory objective 5

To evaluate BCR repertoires and sequences of the BG505-specific GC and memory B cells

Exploratory objective 6

To evaluate CD4+ T-cell mapping and HLA typing by BG505 MD39.3 trimer mRNA vaccines in a subset of participants

Exploratory objective 7

To evaluate the ability of the vaccine regimen to elicit HIV-1 specific heterologous tier 2 neutralizing antibodies

Exploratory objective 8

To characterize monoclonal antibodies derived from BCR sequences from BG505-specific B cells

Exploratory objective 9

To characterize antibody avidity and Fc-mediated antibody functions (eg, antibody-dependent cellular phagocytosis [ADCP] and antibody-dependent cellular cytotoxicity [ADCC])

Exploratory objective 10

To evaluate binding antibody responses elicited by BG505 MD39.3 trimer mRNA vaccines as measured via ELISA

Additional exploratory objectives

To conduct analyses related to furthering the understanding of HIV, immunology, vaccines, and clinical trial conduct. To further evaluate immunogenicity of each vaccine regimen, additional immunogenicity assays may be performed in a subset of participants, including on samples from other timepoints, based on the HVTN Laboratory Assay Algorithm.

4 Laboratory strategy

The primary goal of HVTN 302 is to determine whether the BG505 MD39.3 HIV trimer mRNA vaccines can drive the induction of tier 2 serum neutralizing antibody responses. To this end, HVTN immunogenicity assays will be used to evaluate induction of autologous and heterologous neutralization as well as vaccine and epitope-specific binding antibodies. These data will also be used to identify and prioritize samples for in-depth immunogenicity analyses, including epitope-mapping of serum neutralizing antibody responses, and isolation and characterization of neutralizing monoclonal antibodies. Germinal center B cells and T cells will be evaluated in fine needle aspirates from lymph nodes to assess the impact of the different immunogen modalities and modifications (such as aberration of CD4 binding) in the trafficking and retention of antigen in the draining lymph nodes and degree of germinal center activity. The detailed laboratory strategy is described in the Central Assay Plan and will be updated as new reagents and techniques are incorporated into assay planning. This document will be available on the protocol webpage. Descriptions of the standard HVTN laboratory assays can be found online at <https://www.hvtn.org/content/dam/hvtn/scientific-programs/hvtn-laboratory-assay-descriptions.pdf>.

5 Study design

This is a multicenter, randomized, open-label, Phase 1 study to evaluate the safety and immunogenicity of BG505 MD39.3, BG505 MD39.3 gp151, and BG505 MD39.3 gp151 CD4KO HIV trimer mRNA in healthy adults. The primary hypothesis is BG505 MD39.3 soluble and membrane-bound trimer mRNA vaccines will be safe and well-tolerated among HIV-uninfected individuals and will elicit autologous neutralizing antibodies.

5.1 Study population

All inclusion and exclusion criteria must be met for eligibility. Screening procedures to determine eligibility must be performed within 56 days prior to enrollment.

Investigators should always use good clinical judgment in considering a volunteer's overall fitness for trial participation. Some volunteers may not be appropriate for enrollment even if they meet all inclusion/exclusion criteria. Medical, psychiatric, occupational, or other conditions may make evaluation of safety and/or immunogenicity difficult, and some volunteers may be poor candidates for retention.

5.1.1 Inclusion criteria

1. Able and willing to complete the informed consent process, including an Assessment of Understanding: volunteer demonstrates understanding of this study; completes a questionnaire prior to first vaccination with verbal demonstration of understanding of all questionnaire items answered incorrectly.
2. 18-55 years old, inclusive, on day of enrollment.
3. Agrees to comply with planned study procedures and be available for clinic follow-up through the last clinic visit.
4. Agrees not to enroll in another study of an investigational agent during participation in the trial. If a potential participant is already enrolled in another clinical trial, approvals from the other trial sponsor and the HVTN 302 PSRT are required prior to enrollment into HVTN 302.
5. In good general health according to the clinical judgement of the site investigator.
6. Physical examination and laboratory results without clinically significant findings that would interfere with assessment of safety or reactogenicity in the clinical judgement of the site investigator.

7. Assessed as low risk for HIV acquisition per low risk guidelines (see [Appendix H](#)), agrees to discuss HIV infection risks, agrees to risk reduction counseling, and agrees to avoid behavior associated with high risk of HIV exposure through the final study visit. Low risk may include persons stably taking pre-exposure prophylaxis (PrEP) as prescribed for 6 months or longer.
8. Hemoglobin
 - ≥ 11.0 g/dL for volunteers who were assigned female sex at birth
 - ≥ 13.0 g/dL for volunteers who were assigned male sex at birth and transgender males who have been on hormone therapy for more than 6 consecutive months
 - ≥ 12.0 g/dL for transgender females who have been on hormone therapy for more than 6 consecutive months
 - For transgender participants who have been on hormone therapy for less than 6 consecutive months, determine hemoglobin eligibility based on the sex assigned at birth
9. White blood cell (WBC) count $> 3,500/\text{mm}^3$
10. Platelets $\geq 125,000 / \text{mm}^3$
11. Alanine aminotransferase (ALT) $< 2.5 \times$ upper limit of normal (ULN) based on the institutional normal range
12. Serum creatinine $\leq 1.1 \times$ ULN based on the institutional normal range
13. Negative results for HIV infection by an (US) Food and Drug Administration (FDA)-approved enzyme immunoassay (EIA) or chemiluminescent microparticle immunoassay (CMIA).
14. Negative for anti-Hepatitis C antibodies (anti-HCV) or negative HCV nucleic acid test (NAT) if anti-HCV antibodies are detected.
15. Negative for Hepatitis B surface antigen.
16. For a volunteer capable of becoming pregnant:
 - Volunteers who were assigned female sex at birth and are of reproductive potential must agree to use effective means of birth control from at least 21 days prior to enrollment through 3 months after their third vaccination timepoint (see [Appendix I](#))

- Has negative β -HCG (beta human chorionic gonadotropin) pregnancy test (urine or serum) at screening and prior to study product administration on day of enrollment.

